[name], Director of York Trials Unit, [name]. [contact], [contact], [contact]

Contents

1. Trial Synopsis	3
2. Background and Rationale	5
3. Aims and Objectives	7
4. Study Design	9
5. Patient Eligibility and Participation	.13
6. Trial Evaluations	16
7. Health Economic Assessment	22
8. Statistical Considerations	23
9. Pharmacovigilance	24
10. Research Governance	27
11. Ethics, Confidentiality and Liability	. 30
12. The Study Team	31
Deferences	21

1. Trial Synopsis

Patients with Chronic Heart Failure (CHF) commonly have significant limiting symptoms despite optimal management. The prevalence and clinical relevance of hypoxaemia in patients with CHF is incompletely understood. Currently, Home Oxygen Therapy (HOT), in various forms, is used commonly despite the absence of evidence of benefit.

The present study seeks to address the uncertainties surrounding home oxygen therapy for patients with chronic heart failure who are still severely symptomatic despite maximally tolerated medical therapy. The study will randomise 450 patients equally to its active treatment arms. These are (a) best medical therapy without oxygen (b) best medical therapy with daytime Long Term Oxygen Therapy (LTOT for at least 15 hours per day in the home, including overnight hours) or (c) best medical therapy with Nocturnal Oxygen Therapy (NOT overnight in the home). Each patient will remain within the study for at least 1 year. All patients will continue active treatment within the study until the last patient recruited has completed their 1 year's active treatment, meaning that the first patient recruited will remain on active treatment for approximately 2 years in total. Patients can withdraw at any point, and such incidences will be included within the quality of life analysis.

Primary Research Question

Is there a quality of life benefit from home oxygen therapy given as either long term daytime or nocturnal oxygen therapy compared with best medical therapy in patients with stable severely symptomatic chronic heart failure?

Primary Objectives

 To assess the quality of life benefits of home oxygen therapy in the management of patients with stable CHF who are still severely symptomatic despite maximally tolerated medical therapy.

Secondary Objectives

- To assess the prevalence of hypoxaemia in patients with NYHA III/IV symptoms and optimal medical therapy in order to answer the questions: (a) do patients with stable CHF have arterial hypoxaemia? (b) if so, is this when awake or asleep? and (c) what are its clinical correlates?
- To assess the effect of home oxygen therapy (HOT), delivered as either NOT or LTOT, on symptoms, and disease severity in patients with CHF
- To assess the cost-effectiveness of HOT
- To assess the acceptability to patients and carers of HOT.

Eligibility

The eligibility criteria are as follows:

Inclusion Criteria

- Provided written informed consent and able to complete patient assessments.
- Aged 18 years or over.

Patients with/who are/have:

- Heart failure from any aetiology.
- Heart failure grade NYHA III/IV with left ventricular (LV) systolic dysfunction confirmed by echocardiography. The left ventricular ejection fraction must be less than 40% or graded as at least "moderately" impaired on visual inspection if an accurate ejection fraction cannot be calculated.
- Receiving maximally tolerated medical management of their heart failure
 - Reached target dose (or be on maximally tolerated dose of, or be intolerant of) an inhibitor of the renin angiotensin system shown to improve prognosis
 - Reached target dose (or be on maximally tolerated dose of, or be intolerant of) a beta adrenoceptor antagonist shown to improve prognosis
 - Reached target dose (or be on maximally tolerated dose of, or be intolerant of) an aldosterone antagonist

Exclusion Criteria

Patients who:

- Are unable to provide written informed consent.
- Have had a CRT device implanted within the previous 3 months
- Have co-existing malignant disease if this would affect the study in the investigators' opinion.
- With interstitial lung disease
- Have COPD likely to fulfil criteria for LTOT; FEV1/FVC <70% and FEV1<40% predicted and hypoxia (pO₂ <7.3kPa or saturations <90%)
- Are using any device or medication that would impede their ability to use LTOT or NOT, such as CPAP
- Are unwilling or unable to comply with safety regulations regarding oxygen use, particularly smoking
- Are unable to complete patient related information on entry.

2. Background and Rationale

The standard medical therapy of diuretics for fluid retention and angiotensin converting enzyme inhibitors (ACE-I) or angiotensin-II blockers (A2B) together with beta-blockade (if tolerated) and aldosterone antagonism has resulted in major improvements in mortality and morbidity for patients with chronic heart failure (CHF). However, many patients live for many years with a considerable symptom burden. Breathlessness and fatigue are the two major symptoms and help form the basis of the clinical classification of heart failure severity; the New York Heart Association (NYHA) class of symptoms. Indeed, the presence of symptoms is part of the definition of the heart failure syndrome.

Oxygen therapy is an established part of the management of acute pulmonary oedema complicating heart failure, but its place is less clear in patients with stable compensated CHF. Whilst patients with acute pulmonary oedema undoubtedly have hypoxaemia (low blood oxygen), there are conflicting reports from patients with CHF; whilst some report mild degrees of hypoxaemia, others report that patients with CHF have normal or even higher than normal levels of arterial oxygen.^{2 3 4 5 6 7}

A complicating issue is that of sleep disordered breathing (SDB), which appears to be common in patients with CHF.⁸ SDB is commonly due to *obstructive* sleep apnoea (OSA) in which collapse of the upper airways during sleep results in obstruction to airflow and hypoxia and arousal. It is typically seen in overweight middle-aged men. In patients with CHF, SDB is commonly *central sleep apnoea* (CSA) and results in a cyclical breathing pattern between episodes of apnoea (and thus hypoxaemia) and over-breathing, sometimes accompanied by arousal. CSA is more common in patients with CHF than in those without. It is associated with disturbed sleep, daytime sleepiness and risk of arrhythmia. However, the contemporary prevalence is unclear; previous studies were done before current medication was routinely used, and case series reports have since suggested that optimisation of medical therapy, selected use of devices (such as resynchronisation) and transplantation reduces CSA.⁹ 10 11

Home oxygen therapy (HOT), an expensive treatment which is potentially burdensome for patients and carers, is often prescribed for patients with chronic heart failure, although it is unknown whether it is of benefit in the medium to long-term with regard to symptoms, severity of CHF, hospitalisation or survival. Also unknown, assuming oxygen is of benefit, is how it should be administered; short burst oxygen therapy (SBOT), nocturnal (NOT) or long-term (LTOT). In addition to the concern that there is no proven benefit from oxygen, some reports suggest that hyperoxia leads to clinically significant adverse haemodynamic effects such as increased vascular resistance, left ventricular filling pressure, blood pressure and reduced cardiac output due to the formation of oxygen free radicals.¹²

There are only a few, small, unpowered studies looking at the effect of short term SBOT on breathlessness and exercise tolerance in a variety of conditions. Those trials that randomised patients did not confirm benefit. A large observational study of patients with breathlessness of varying aetiology concluded that oxygen therapy was of no benefit for symptom relief in the absence of hypoxaemia, a finding echoed in a Cochrane review. A recent double blind placebo controlled study confirmed that oxygen was no better than placebo for the relief of intractable breathlessness in study participants, a few of whom had CHF.

The benefits for mortality and morbidity of LTOT in patients with chronic obstructive pulmonary disease and hypoxia are well established,¹⁷ but dependent upon good compliance. One study has suggested that there is less than 30% compliance with prescribed therapy.¹⁸ LTOT (>15 hours per day) has not been studied in patients with left ventricular dysfunction or CHF. The criteria which should be used to assess suitability of LTOT in patients with CHF, let alone benefit in terms of survival, severity of disease or symptomatology is unknown. It is also unknown whether CHF patients would tolerate the intervention which would be more intrusive than NOT alone.

NOT has been studied in small randomised trials in patients with CHF with a maximum follow-up of 3 months¹⁹ ²⁰ ²¹ ²² ²³ and appears to reduce CSA and nocturnal sympathetic activity; evidence of improvement either of cardiac function or symptoms is inconsistent.

3. Aims and Objectives

The aim of the study is to determine if the addition of home oxygen therapy (given either during the day or night) improves life quality for patients with stable, severely symptomatic chronic heart failure, who are already receiving best medical therapy.

3.1 Primary Research Question

• Is there a quality of life benefit from home oxygen therapy given as either long term or nocturnal oxygen therapy compared with best medical therapy in patients with stable severely symptomatic chronic heart failure?

3.2 Primary Objectives

 To assess the quality of life benefits of home oxygen therapy in the management of patients with stable CHF who are still severely symptomatic despite maximally tolerated medical therapy. That is, do patients with chronic heart failure (CHF), with or without hypoxaemia, benefit from home oxygen therapy (HOT), given as Nocturnal Oxygen Therapy (NOT) or Long Term Oxygen Therapy during the day (LTOT)?

3.3 Primary Endpoint

Effect of different oxygen therapies (LTOT, NOT or no oxygen therapy) on quality
of life as measured by change in the Minnesota Living with Heart Failure
(MLWHF) score at one year.

3.4 Secondary Objectives

- To assess the prevalence of hypoxaemia in patients with NYHA III/IV symptoms and optimal medical therapy in order to answer the questions: (a) do patients with stable CHF have arterial hypoxaemia? (b) if so, is this when awake or asleep? and (c) what are its clinical correlates?
- To assess the effect of home oxygen therapy (HOT), delivered as either NOT or LTOT, on symptoms, and disease severity in patients with CHF
- To assess the cost-effectiveness of HOT
- To assess the acceptability of HOT to patients and carers

3.5 Secondary Endpoints

- 1. Mortality
- 2. Number of days alive and out of hospital
- 3. Symptomatic status measured by
 - a. Health-related quality of life as measured by the Euroqol 5D instrument (EQ-5D)
 - Severity of and distress caused by breathlessness as measured by the Numerical Rating Scale (NRS) for breathlessness (average and worse over past 24 hours and global change in breathlessness)
 - c. Patient satisfaction measured by NRS (in addition to interviews as part of qualitative study)
 - d. Epworth Sleepiness score to assess daytime somnolence
 - e. Mood using the HAD score
- 4. Severity of heart failure assessed by
 - a. Severity of left ventricular dysfunction on echocardiogram
 - b. Nt-proBNP
- 5. Exercise capacity assessed by
 - a. Karnofsky performance scale of physical activity
 - b. 6 minute walk test
- 6. Prevalence of hypoxia measured as
 - a. Resting hypoxia
 - b. Hypoxia during 6 minute walk test
 - c. Nocturnal oxygen saturation and presence of SDB
- 7. Number of hours of oxygen used measured by concentrator meter.
- 8. Co-morbidity measured by the Charlson co-morbidity index
- 9. Cost-effectiveness

4. Study Design

4.1 Design

This is a phase 3, prospective, multi-centre, randomized, parallel-group, controlled trial in patients with stable NYHA Grade III/IV heart failure receiving optimal medical therapy. 450 eligible patients will be allocated by block randomisation 1:1:1 to one of the three limbs of the study, to receive for a period of at least one year, either (a) best medical therapy without home oxygen treatment; (b) best medical therapy with Long Term home Oxygen Therapy (daytime LTOT, for at least 15 hours per day); or (c) nocturnal oxygen therapy (NOT, at least 8 hours per night).

Although the primary end-point of the study is one-year quality of life, data are also to be collected at 3 months during a home visit by the study nurse in order to detect any transient change in quality of life that is lost later. All patients will be asked to continue in the trial with 6-monthly assessments until the last patient recruited has finished one year's participation in the trial. This allows the trial to address quality of life changes and cost effectiveness (the primary outcome), and also to make a provisional assessment of the effect on clinical outcomes, and associated cost effectiveness.

HOT Trial Summary Flow Chart

Patient identification from database, heart failure nurse case list, or treating physician

↓

Eligibility Criteria Fulfilled

↓

Informed Consent

↓

Pandomisation to one of 3 Groun

Simple Randomisation to one of 3 Groups

Baseline Data Collection

Medical Therapy + NOT Medical Therapy + LTOT

Assessments at Baseline, 3 months & 6 monthly thereafter for 1 year, or until the last patient has completed, up to a maximum of 2 years.

Study End with Assessment of Patient for Further NHS Oxygen Therapy

There will be a nested, qualitative, single centre sub-study involving semi-structured interviews with a purposive sample of patients in each arm of the study to explore the views and experience of participants and their carers regarding oxygen therapy. An entirely separate, single centre sub-study will assess the acute effect of oxygen on haemodynamics in patients with CHF.

4.2 Problems of a Placebo Controlled Study

The investigators considered including a 'placebo' sham oxygen concentrator arm in order to tease out a 'quality of life' placebo effect associated with the presence of a concentrator. The sham concentrator would deliver normal room air instead of air with increased concentration of oxygen, This approach, however, suffers from analytical and practical problems.

Analytically, it is difficult to separate the extent of any change in symptoms because there will be a combination of potential effects from the oxygen therapy itself and the effect associated with prolonged use of nasal cannulae and concentrators, complicating comparison across the trial arms. In other words, it would not be possible to detect what proportion of any quality of life impact is due to the placebo effect of the device, versus the intrusive effect of the nasal cannulae. Hence, the investigators decided on an open label design to allow comparison with a group of patients treated with best medical therapy.

Secondly, the act of using the concentrator may be beneficial by increasing air flow across the face: by stimulating the upper airway receptors, it may thereby alleviate the symptoms of breathlessness.²⁴ The sham treatment may thus have a 'true', clinically demonstrable, beneficial effect, further complicating comparison.

Finally, motivated patients could easily unblind the study (for example, by holding a smoldering match near the concentrator to see if it re-ignited), and would have plentiful opportunity to do so, since the concentrators are in their homes. Crucially, for the trial, it would be very difficult to know whether individual patients had unblinded the study.

Practically, there are several financial, legal, regulatory and logistical problems associated with the use of a placebo machine. The use of 'sham devices' requires the manufacture of specially modified and marked devices, to sit alongside similarly marked standard devices within separate storage facilities, managed under separate legal contracts, and requiring regulatory approval at both national and local Trust levels. This dramatically increases the costs and complexity of delivering the trial, while reducing our ability to recruit patients from different centres, and increasing delays. The research team has spent some 18 months attempting to overcome these hurdles.

For these reasons, the investigators have decided to opt for an open three-armed treatment trial: any effect of the intervention will thus be a "real world" estimate of any benefit from oxygen therapy, including an estimate of any placebo effect.

4.3: Problems of Stratification by Hypoxaemia.

The research team have considered stratification by hypoxia, but have rejected it on the advice of both the HTA monitors and the Trial Steering Committee. The true prevalence of hypoxaemia in patients with chronic heart failure is not known, but from the available evidence, the investigators suspect that it is very low. However, it is certainly possible that some patients have minor degrees of hypoxaemia (in the range of 92 - 96%) and may benefit; it is also likely that patients have hypoxaemia overnight.

Given that home oxygen therapy is commonly prescribed for heart failure patients on the basis of symptoms rather than on the basis of hypoxaemia, the investigators did not want to risk limiting recruitment by insisting on a qualification based on an arbitrary level of hypoxaemia. The researchers will, however, analyse the data based on pre-treatment hypoxaemia.

4.4 Trial Timeline

Setup - 3 months (1 April 2011 – 30 June 2011)

IRAS approvals (MREC & CSP)
Completion of any additional licensing & approvals
Start 3 & 6 monthly TMG, TSC & DMEC cycles
Update and establish trial materials & database
Train centre teams
Start of systematic health economic review
Development of preliminary cost-effectiveness model

Recruitment - 12 months (1 July 2011 – 30 June 2012)

Commence patient recruitment and data collection Monitor and support patient recruitment and retention Launch and complete Qualitative & Oxygen sub studies

Follow Up - 24 months (ends 30 June 2013)

Maintain data collection at centres.

Address data problems that arise to avoid delays to subsequent stages.

Analyse and present initial Qualitative and Oxygen sub study findings.

Data Cleaning - 3 months (1 July – 30 September 2013)

Analysis - 3 months (1 October 2013 – 31 December 2013)

Write Up of Trial Report - 3 months (1 January – 31 March 2013)

Submission of HTA Draft Report – 14 days (15 April 2014)

Publish findings for the Main study, Qualitative and Oxygen sub studies.

5. Patient Eligibility and Participation

5.1 Patient Numbers and Identification

Four hundred and fifty (450) patients will be recruited into the study over a period of 1 year. Participating centres have large cohorts of eligible patients, who are already receiving long term CHF care, supporting the screening of case lists. Patients may also be detected incidentally, though specific heart failure, general cardiology or general clinics, or through inpatient admissions. It is anticipated that the bulk of patients will be identified through clinic-based case-finding of existing patient cohorts.

It is anticipated that the trial will recruit from a large number of centres, over a period of one year, with each centre expected to recruit at least 10 patients.

The symptom burden and prognostic impact of the illness are high in patients with severe symptoms, and such patients have potentially the most to gain from oxygen therapy if it is beneficial. Patients can continue oxygen treatment at the end of the trial if they have found it beneficial.

5.2 Eligibility Criteria

5.2.1 Inclusion Criteria

- Provided written informed consent and able to complete patient assessments.
- Aged 18 years or over.

Patients with/who are/have:

- Heart failure from any aetiology.
- Heart failure grade NYHA III/IV with left ventricular (LV) systolic dysfunction confirmed by echocardiography. The left ventricular ejection fraction must be less than 40% or graded as at least "moderately" impaired on visual inspection if an accurate ejection fraction cannot be calculated.
- Receiving maximally tolerated medical management of their heart failure
 - Reached target dose (or be on maximally tolerated dose of, or be intolerant of) an inhibitor of the renin angiotensin system shown to improve prognosis
 - Reached target dose (or be on maximally tolerated dose of, or be intolerant of) a beta adrenoceptor antagonist shown to improve prognosis
 - Reached target dose (or be on maximally tolerated dose of, or be intolerant of) an aldosterone antagonist

5.2.2 Exclusion Criteria

Patients who:

- Are unable to provide written informed consent.
- Have had a CRT device implanted within the previous 3 months
- Have co-existing malignant disease if this would affect the study in the investigators' opinion.
- Patients with persistent basal pulmonary crackles found to have interstitial lung disease
- Have COPD likely to fulfil criteria for LTOT; FEV1/FVC <70% and FEV1<40% predicted and hypoxia (pO₂ <7.3kPa or saturations <90%)
- Are using any device or medication that would impede their ability to use LTOT or NOT, such as CPAP
- Unwilling or unable to comply with safety regulations regarding oxygen use, particularly smoking
- Are unable to complete patient related information on entry.

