11.1 Ethical Considerations

The patient population under study is a potentially vulnerable group and care should be taken not to introduce further physical, psychological or financial burden with entry into studies. However, this must be balanced with the need to test practices that are potentially beneficial or unhelpful or burdensome. In order to try to address some of these concerns, this study:

- Includes a research team with a broad base of clinical experience including palliative care and psychology and includes a qualitative component to access patient views
- Minimises the need for hospital visits, by employing sufficient research nurses to allow home visits for follow- up
- Uses assessments kept to short form and non-invasive techniques
- Will reimburse reasonable travel costs
- Provides support for participants as part of research nurse role
- Allows continuation of the treatment if perceived to be beneficial to that patient once follow-up has been completed
- It is recognised that some participants will be in a position of clinical dependence with some of the research team as patients under their care. GCP procedures with regard to consent will be observed.

Patients for whom there is a proven clinical indication (such as patients with COPD and hypoxia) are excluded from the trial. Patients randomised to receive oxygen therapy who find it beneficial, can continue on this therapy at the end of the trial period.

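### Read plainly, the COPD exclusion requires FEV1 below 40% predicted as well as hypoxia, so hypoxic COPD with a higher FEV1 is excluded only by clinical judgement, although section 11.1 says patients with COPD and hypoxia are excluded

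*Protocol*

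**What the plan says.** The operative criterion is in section 5.2.2 and is repeated in the same words in the section 1 synopsis. It opens with "Have COPD likely to fulfil criteria for LTOT" and, after a semicolon, gives "FEV1/FVC <70% and FEV1<40% predicted and hypoxia". A bracket then defines hypoxia as pO2 <7.3 kPa or saturations <90%.

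Two other places bear on who this is meant to remove:

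- Section 11.1: "Patients for whom there is a proven clinical indication (such as patients with COPD and hypoxia) are excluded from the trial".
- Section 2: "The benefits for mortality and morbidity of LTOT in patients with chronic obstructive pulmonary disease and hypoxia are well established".

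Neither gives an FEV1 limit, and the protocol nowhere explains the 40% figure.

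On allocation, section 4.1 states: "450 eligible patients will be allocated by block randomisation 1:1:1 to one of the three limbs of the study". The three arms are no home oxygen, LTOT for at least 15 hours a day, and nocturnal oxygen for at least 8 hours a night, for at least one year.

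**The concern.** The ethics section gives a broad assurance: patients with COPD and hypoxia do not enter, because oxygen is already indicated for them. The criterion that sites apply is narrower on its plain reading, because it adds severe airflow obstruction as a further requirement.

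Two things are at stake. First, a patient whom section 11.1 describes as excluded could be randomised to no oxygen or to nocturnal oxygen only. Second, sites could differ. One may apply the numeric thresholds as the definition, and another may treat them as a guide and exclude on the lead phrase. The protocol expects a large number of centres (section 5.1) and does not say which reading governs.

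**Working it through.** No formula underlies the criterion, so the check sets the texts side by side.

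**Inputs.** From section 5.2.2:

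- A: FEV1/FVC <70%
- B: FEV1 <40% predicted
- C: pO2 <7.3 kPa or saturations <90%

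From section 11.1: COPD with hypoxia.

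**Step 1: the rules as logic.** Section 5.2.2, read as a conjunction, excludes A and B and C. Section 11.1 describes COPD and C as excluded. The gap is COPD with A and C but not B.

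**Step 2: an illustrative patient.** Take COPD with FEV1/FVC 60%, FEV1 50% predicted and pO2 7.0 kPa (values chosen only to show the logic).

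| Text | Result |
|---|---|
| 5.2.2, all three conditions required | A met, B not met, C met: not excluded |
| 5.2.2, lead phrase governs and the figures are a guide | excluded if the clinician judges that LTOT criteria are likely to be met |
| 11.1 | excluded |

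**Step 3: the other exclusions.** The rest of section 5.2.2 covers consent, recent CRT, malignancy, interstitial lung disease, devices or medication that impede oxygen use, oxygen safety, and inability to complete patient information. None of these removes the patient.

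**Step 4: consequence per patient.** Under 1:1:1 allocation:

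- P(no oxygen) = 1/3
- P(nocturnal oxygen only) = 1/3
- P(arm without LTOT) = 1/3 + 1/3 = 2/3, about 0.67

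**Step 5: how many patients.** This cannot be computed. The protocol gives no COPD prevalence and no FEV1 distribution. On hypoxaemia, section 4.3 states: "The true prevalence of hypoxaemia in patients with chronic heart failure is not known". It adds that the investigators suspect the prevalence is very low. Patients who also have COPD and an FEV1 of 40% or more can only be a subset of those.

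**The case against.** The strongest reply is that the lead phrase already covers the case. A clinician who thinks a hypoxic COPD patient with an FEV1 of 45% would qualify for LTOT can exclude that patient on those words. This stands, and it is why the texts do not flatly contradict each other, as a reader might infer. It does not settle the matter, because thresholds placed straight after a semicolon read as the definition of the phrase, and the protocol gives no other LTOT criteria.

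Section 11.1 is also a summary in an ethics paragraph. It repeats none of the thresholds, so its silence on FEV1 does not prove an intention to drop the limit. That too stands. It is still the protocol's stated commitment, and the criterion should deliver it or the statement should be qualified. Likewise, section 2 is a one-sentence background statement, and the protocol does not say whether the evidence it cites covers patients with FEV1 of 40% or more.

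The 40% limit could be deliberate, meant to keep patients whose hypoxaemia comes mainly from heart failure with incidental mild obstruction. The trial does study hypoxaemia and plans to use it: "The researchers will, however, analyse the data based on pre-treatment hypoxaemia". This is possible, but the protocol does not say so.

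A reader might also infer that such patients would go without LTOT for a full year. The protocol does not support that. Consultants are responsible for eligibility (section 10.1), the treating physician can withdraw a patient, and the patient can leave at any time (section 5.5). Withdrawal, however, acts only after entry.

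**Conclusion.** The point holds as an ambiguity in the operative criterion, which on its plain reading is narrower than the commitment in section 11.1. Hypoxic COPD with FEV1 of 40% predicted or more is excluded only if the clinician relies on the lead phrase. For any such patient randomised, the chance of an arm without LTOT is 2/3.

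This rests on the conjunctive reading of the three conditions, and on taking sections 2 and 11.1 at their word that COPD with hypoxia is an established indication.

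It is a minor matter of patient protection and uniform eligibility. A reader might infer bias in the quality-of-life comparison or a need to revise the sample size. Nothing in the protocol supports either: the number affected is unknown and probably very small, and the sample size calculation in section 8.1 does not depend on this criterion.

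**What to change.** In sections 1 and 5.2.2, reword the exclusion so that FEV1 <40% is no longer a necessary condition, for example:

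> COPD (FEV1/FVC <70%) with hypoxia (pO2 <7.3 kPa or saturations <90%), or COPD otherwise likely to qualify for LTOT, whatever the FEV1.

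This keeps room for clinical judgement and matches section 11.1. If the investigators do intend the 40% limit, the alternative is to keep it, give the reason, and qualify section 11.1 accordingly.

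**Cost.** One line changes in two places. No new test is needed: the remaining conditions are already in the criterion, and spirometry and pulse oximetry are already baseline assessments (section 6.3).

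The change does narrow eligibility. A probably small but not computable number of hypoxaemic patients with COPD and milder obstruction would become ineligible. That slightly thins the analysis by pre-treatment hypoxaemia (section 4.3) and possibly the one by baseline mean nocturnal saturation (section 8.2).

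The added hypoxia limb is confined to COPD with saturations <90% or pO2 <7.3 kPa. Nobody without COPD is affected. On saturation alone, that limb does not reach the group of whom section 4.3 says "some patients have minor degrees of hypoxaemia (in the range of 92 - 96%) and may benefit".
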